9.4.1.3 Other Efficacy Endpoint Analysis

The other efficacy endpoints are as follows. All of them will be evaluated at a nominal 0.05 level (2-sided) without adjusting for multiplicity on Efficacy Sample:

- 1) Change from baseline to Weeks 2 and 4 in IDS-SR-10-engagement.
- 2) Change from baseline to Weeks 2 and 4 in IDS-SR Total score.
- 3) Change from baseline to Weeks 2, 4, and 8 in IDS-SR patient-selected engagement items.
- 4) Change from baseline to Weeks 2, 4, and 8 in IDS-SR engagement items selected by both clinicians and patients.
- 5) Change from baseline to Weeks 2, 4, and 8 in CGI-S score.
- 6) CGI-I score at Weeks 2, 4, and 8.
- 7) Change from baseline to Weeks 4 and 8 in SDS Mean score and SDS individual item scores.
- 8) Change from baseline to Weeks 4 and 8 in WHODAS 2.0 short form score.
- 9) Change from baseline to Weeks 2, 4, and 8 in PHQ-9 score.
- 10) Change from baseline to Weeks 2, 4, and 8 in GAD-7 score.
- 11) Change from baseline to each timepoint (ie, being measured weekly at home) in depression as measured by PGI-I score.

- 12) PGI-I response rate at each timepoint (ie, being measured weekly at home), where response is defined as a PGI-I score of 1 or 2 (very much improved or much improved).
- 13) Time to first PGI-S response, where response is defined as a reduction of 2 points in PGI-S score from baseline.

Endpoint (1) - (5), (7) - (11) will be analyzed by fitting the same MMRM model described in the primary analysis on OC dataset. Endpoint (6) will be analyzed using one-sample t-test on LOCF dataset. Endpoint (12) will be evaluated using descriptive statistics on LOCF dataset. Endpoint (13) will be evaluated by time-to-event analysis with Kaplan-Meier curve on OC dataset.

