#### 4 Sample Size

This is a single-arm trial to assess the effect of brexpiprazole on patient engagement in MDD patients through the following co-primary endpoints: 1) change from baseline to Week 8 in IDS-SR-10-engagement; 2) change from baseline to Week 8 in IDS-SR Total score.

Based on the results of the appropriate brexpiprazole-plus-ADT arms from four previous Phase 2/3 brexpiprazole MDD trials, it is reasonable to expect a mean change of -2.5 (standard deviation = 6.5) in IDS-SR-10-engagement and a mean change of -5 (standard deviation = 13.5) in IDS-SR Total score from baseline to Week 8. A sample size of 100 completers (ie, patients who have an evaluation on IDS-SR Total score and IDS-SR-10-engagement at Week 8) will yield 95% power to show a difference from baseline in IDS-SR Total score and at least 95% power to show a difference from baseline in IDS-SR-10-engagement at a two-sided significance level of 0.05, respectively. It will ensure the overall power is at least 90%. After considering an ET rate of 25%, a total of 134 patients needs to be enrolled in this trial.

It is anticipated that approximately 210 patients will be screened in order to enroll 134 subjects from approximately 15 sites (to complete 100 patients).

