The last observation carried forward (LOCF) approach will also be used to impute missing data for continuous and categorical efficacy endpoints. The LOCF data set will include data recorded at a scheduled visit during the open-label treatment phase or, if no observation is recorded at that visit, data carried forward from the previous scheduled visit at the open-label treatment phase. Baseline data will not be carried forward to impute missing values for the LOCF data set.

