#### 8.2 Other Efficacy Endpoint Analysis

The other efficacy endpoints are as follows. All of them will be evaluated at a nominal 0.05 level (2-sided) without adjusting for multiplicity on Efficacy Sample:

[figure not shown]
- 1) Change from baseline to Weeks 2 and 4 in IDS-SR-10-engagement
- 2) Change from baseline to Weeks 2 and 4 in IDS-SR Total score
- 3) Change from baseline to Weeks 2, 4, and 8 in IDS-SR patient-selected engagement items
- 4) Change from baseline to Weeks 2, 4, and 8 in IDS-SR engagement items selected by both clinicians and patients.
- 5) Change from baseline to Weeks 2, 4, and 8 in CGI-S score
- 6) CGI-I score at Weeks 2, 4, and 8
- 7) Change from baseline to Weeks 4 and 8 in SDS Mean score and SDS individual item scores
- 8) Change from baseline to Weeks 4 and 8 in WHODAS 2.0 short form score.
- 9) Change from baseline to Weeks 2, 4, and 8 in PHQ-9 score
- 10) Change from baseline to Weeks 2, 4, and 8 in GAD-7 score
- 11) PGI-I score at each timepoint (ie, being measured weekly at home)

- 12) PGI-I response rate at each timepoint (ie, being measured weekly at home), where response is defined as a PGI-I score of 1 or 2 (very much improved or much improved)
- 13) Time to first PGI-S response, where response is defined as a reduction of 2 points in PGI-S score from baseline.

Endpoint (1) - (5), (7) - (10) will be analyzed by fitting the same MMRM model described in the primary analysis on OC dataset. Endpoints (6) and (11) will be analyzed using one-sample t-test on LOCF dataset, with the null hypothesis of no change in each of the endpoints. The point estimate with 95% CI will be provided for endpoint (12) using normal approximation on LOCF dataset. Endpoint (13) will be evaluated by time-to-event analysis with Kaplan-Meier curve on OC dataset. The time origin for measuring this event time is the date of the first dose of open-label brexpiprazole. The event date will be the date when a reduction of 2 points in PGI-S score from baseline is achieved.

Version Date: 29 Jun 2022

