#### 11 Conventions

#### 11.1 Trial Visit Windows

Study visit windows will be used to map visits using study day intervals. The derived study window variable will be named as WEEK and will be footnoted. In listings it will be listed along with the eCRF study visit. The visit window convention shown in Table 11.1-1 is applied to tables and listings for efficacy scales, including IDS-SR, PHQ-9, GAD-7, WHODAS2.0, SDS, CGI-S, and CGI-I. The visit window convention shown in Table 11.1-2 is applied to patient diary entries, including PGI-I and 'word of the day'. In each table, the variable "target day" is defined using the number of days since the 1st use of open-label brexpiprazole. The first day of using open-label brexpiprazole is defined as 'Day 1'.

Table 11.1-1 Study Day and Visit Windows for Efficacy Scales (IDS-SR, PHQ-9, GAD-7, WHODAS2.0, SDS, CGI-S, and CGI-I) Target Daya Week Study Day Interval a 2 14 2~20 28 21~41 42-70b 56

<sup>b Evaluations occurring more than seven days after the last open-label brexpiprazole date will be excluded.

Table 11.1-2 Study Day and Visit Windows for Patient Diary Entries (PGI-I, PGI-S and 'Word of the Day')			
Week	Target Day a	Study Day Interval a	
1	2	2-7	
2	9	8-14	
3	16	15-21	
4	23	22-28	
5	30	29-35	
6	37	36-42	
7	44	43-49	
8	51	50-70 b	

<sup>a Relative to the date of 1st use of open-label brexpiprazole.

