#### Patient Global Impression - Improvement (PGI-I) 11.2.12

The Patient Global Impression – Improvement (PGI-I) scale is a 7-point single-item self report scale depicting a patient's rating of overall improvement in their condition since starting trial medication. Patients answer the following question: "Since starting trial medication, how much have your symptoms of Major Depressive Disorder changed?" Scores range from 1 "very much improved" to 7 "very much worse." The PGI-I will be administered weekly throughout the trial.

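### The SAP fixes a normal-approximation 95% interval for the weekly PGI-I response rate, with no alternative for weeks with few responders

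*SAP*

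**What the plan says.** Endpoint 12 is the proportion of patients with a PGI-I score of 1 or 2, at each weekly home assessment. SAP 8.2 sets the method: "The point estimate with 95% CI will be provided for endpoint (12) using normal approximation on LOCF dataset". It does not say which normal-approximation formula is meant, sets no minimum count, and names no exact or score interval as a fallback. SAP 5.2, 11.1 and 11.2.12 do not supply one either.

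SAP 11.2.12 says "The PGI-I will be administered weekly throughout the trial", and Table 11.1-2 in SAP 11.1 gives eight weekly windows, the first covering Days 2 to 7. The interval is therefore to be printed from Week 1.

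Protocol 9.4.1.3 planned less: "Endpoint (12) will be evaluated using descriptive statistics on LOCF dataset". The confidence interval is the SAP's addition. For the whole group of other endpoints SAP 8.2 states: "All of them will be evaluated at a nominal 0.05 level (2-sided) without adjusting for multiplicity on Efficacy Sample".

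**The concern.** The Wald interval takes its width from the observed proportion. When few patients have responded, that width is too small and the interval is centred too close to zero, so it misses the true rate more often than its label says. In the extreme case of no responders it has no width at all.

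Sparse weeks are plausible early on. Response requires at least much improvement, the patients have already responded inadequately to one or two antidepressants, and the Week 1 window closes on Day 7, within the starting-dose week of the dosing schedule. No fallback means that a poor interval would either be printed as planned or be replaced after the counts were seen.

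At stake is the accuracy of a few lines in one table. Those lines do bear on the secondary objective about patients' impression of improvement over time, where the early weeks are of interest. They play no part in the trial's success rule.

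**Working it through.** **Inputs.** SAP 4 gives 100 completers, and "a total of 134 patients needs to be enrolled in this trial" after a 25% early-termination rate. This reproduces: 100 / 0.75 = 133.3, rounded up to 134. The documents give no PGI-I response rate and no weekly PGI-I denominator. So n = 100 and n = 134 are used as working values, and the true rate is varied as an assumption.

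**Formulas**, with z = 1.96, x responders and p = x/n:

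- Wald: p ± z × √(p(1 − p)/n)
- Wilson: [p + z²/(2n) ± z × √(p(1 − p)/n + z²/(4n²))] / (1 + z²/n)
- Exact coverage at true rate π: the sum of binomial(n, π) probabilities over all x whose interval contains π

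**Limits at small counts.** At x = 0 the Wald half-width is 0. The Wilson upper limit is z²/(n + z²): 3.84/103.84 = 3.7% for n = 100 and 3.84/137.84 = 2.8% for n = 134. The Wald lower limit is negative when x < z²(1 − x/n). At n = 100, x = 3 gives 3 < 3.73, so the limit is negative; x = 4 gives 4 > 3.69, so it is positive. The switch also falls between 3 and 4 at n = 134.

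Worked case, x = 3, n = 100: √(0.03 × 0.97/100) = 0.01706; 1.96 × 0.01706 = 0.0334; limits −0.3% to 6.3%.

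| Responders | n | Wald | Wilson |
|---|---|---|---|
| 0 | 100 | 0 to 0% | 0 to 3.7% |
| 0 | 134 | 0 to 0% | 0 to 2.8% |
| 3 | 100 | −0.3 to 6.3% | 1.0 to 8.5% |
| 3 | 134 | −0.3 to 4.7% | 0.8 to 6.4% |
| 30 | 100 | 21.0 to 39.0% | 21.9 to 39.6% |

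**Coverage at single rates** (n = 100 / n = 134):

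| Assumed true rate | Wald | Wilson | Chance of 3 or fewer responders |
|---|---|---|---|
| 1% | 63.3 / 73.9% | 92.1 / 95.4% | 98.2 / 95.4% |
| 2% | 86.6 / 93.2% | 94.9 / 94.7% | 85.9 / 71.9% |
| 3% | 80.2 / 90.6% | 96.9 / 93.4% | 64.7 / 42.7% |
| 5% | 87.7 / 90.0% | 96.6 / 95.5% | 25.8 / 9.3% |
| 10% | 93.2 / 91.4% | 93.6 / 95.8% | 0.8 / under 0.1% |
| 20% | 93.3 / 94.7% | 94.1 / 94.8% | 0 / 0% |

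The first row shows the mechanism. At a true rate of 1% with n = 100, the Wald interval contains 1% only when x is 1 to 5. The chance of x = 0 is 0.99^100 = 36.6%, and that accounts for almost all of the lost coverage.

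**Band averages.** Coverage at a single rate jumps up and down as the rate changes, so averages over 41 equally spaced rates are a fairer summary (n = 100 / n = 134):

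| True rates | Wald | Wilson |
|---|---|---|
| 1–3% | 83.7 / 86.6% | 95.9 / 95.7% |
| 3–5% | 88.5 / 91.0% | 95.5 / 95.4% |
| 5–10% | 91.9 / 92.6% | 95.2 / 95.2% |
| 20–80% | 94.3 / 94.8% | 94.9 / 95.1% |

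**The case against.** Nothing in the documents shows that a sparse week will occur. The trial is open-label and the PGI-I is the patient's own rating of change, so early response may not be rare. This stands: the point is conditional.

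The n = 100 figures may be pessimistic. One hundred is the number of Week 8 IDS-SR completers, while endpoint 12 uses LOCF data in the Efficacy Sample, and dropouts keep their earlier PGI-I values. This stands in part. On the other side, SAP 5.2 says "Baseline data will not be carried forward to impute missing values for the LOCF data set", so a patient with no Week 1 diary entry has no Week 1 value, and the early denominator can fall below 134. The shortfall is milder at n = 134 but remains: average coverage is 86.6% over rates of 1–3%.

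The Wilson interval also rests on a normal approximation, and the SAP does not rule it out. That is true, though Wald is the usual reading of the phrase. If Wilson was meant, naming it settles the matter.

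Finally, no decision uses the interval, and a reader who sees a point estimate near zero will recognise sparse data. This limits the importance of the point. It does not make an interval of 0 to 0% right, and cutting a negative limit off at zero would not restore the coverage.

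**Conclusion.** The concern holds as a minor one. If normal approximation means Wald, the interval is unreliable in any week with few responders. Visible breakdown, meaning zero width or a negative limit, needs 3 or fewer responders and is essentially confined to true rates of about 5% or below. Undercoverage of 2 to 3 percentage points on average persists over rates of 5–10%. At 20% or more there is no practical problem.

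This rests on three assumptions: the Wald reading, weekly denominators of about 100 to 134, and a low response rate in at least one week, for which the documents give no figure. The co-primary analyses and the success rule are unaffected.

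**What to change.** In SAP 8.2, replace the normal approximation for endpoint 12 with the Wilson score method, at all timepoints. Using one method throughout avoids a switch that depends on the observed counts. Clopper-Pearson would also be acceptable but is conservative, with coverage of about 96–99% at true rates of 1–5%.

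The cost is a few words in the SAP and one option in the code, with no change to design or data collection. The Wilson interval is not symmetric about the point estimate, which a table footnote can state. At moderate rates the printed results hardly change.

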### 8.4 Sensitivity analysis

The primary endpoint will be analyzed by Per-Protocol sample. This analyses will be conducted using the same MMRM analysis for the primary efficacy analysis.

## 9 Safety Analyses

All safety analyses will be conducted based upon the Safety Sample. Safety variables to be analyzed include Adverse Events (AEs), body weights, BMI, vital signs, and physical examinations. In general, baseline of a safety variable is defined as the last observation of the variable before taking the first open-label brexpiprazole unless specified otherwise. Prospectively defined criteria will be used to identify potentially clinically relevant abnormal values for vital signs and body weight.

#### 9.1 Extent of Exposure

Duration of exposure is defined as the last day of open-label brexpiprazole - the first day of open-label brexpiprazole +1. The number and percentage of subject who receive open-

label brexpiprazole will be presented biweekly: i.e., Day 1-14 in Week 1-2, Day 15-28 in Week 3-4, etc. The overall exposure will also be provided by summary statistics.

The mean daily dosage will be summarized biweekly using descriptive statistics. The mean daily dosage per patient biweekly will be determined for every two weeks of the

study: ie, Day 1-14 in Week 1-2, Day 15-28 in Week 3-4, etc. This will be calculated by dividing the sum of individual total doses by the number of days in the biweekly interval. The summary will contain the number of patients receiving receive open-label brexpiprazole and the mean and range of the mean daily dose for every two weeks.

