6.4 Patient Compliance

There will be a question in the patient's daily diary asking the patient if they have taken their daily medication. Sites and investigators will assess compliance with patients at the scheduled visits. The actual start and finish dates for each dose strength of trial drug administered will be recorded on the CRF. Information regarding any inappropriately administered dose will also be documented on the CRF.

Patients will be required to comply with medication restrictions outlined in Section 6.5.

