7.3.2 Documenting Reasons for Treatment Interruption or Discontinuation

Brief treatment interruptions/periods of non-adherence will be allowed and managed according to the clinical judgment of the investigators.

A patient may discontinue trial drug for the reasons listed below:

- Adverse event
 - Patient decides to discontinue because of annoyance or discomfort due to a nonserious AE which is not otherwise determined to be an undue hazard
 - Continuing trial drug places the patient at undue risk as determined by the investigator (eg, a safety concern that is possibly, probably, or likely related to trial drug)
 - Serious adverse event (SAE)
 - Other potentially trial drug-related safety concerns or AEs
- Death
- Failure to meet continuation criteria
- Lack of efficacy
- Lost to follow-up
- Noncompliance with trial drug
- Physician decision
- Pregnancy (see Section 10.2)
- Protocol deviation
- Protocol-specific withdrawal criterion met
- Site terminated by sponsor
- Trial terminated by sponsor
- Technical problems
- Withdrawal by patient

• Other

If the patient discontinues trial drug due to an AE, the investigator, or other trial personnel, will make every effort to follow the event until it has resolved or stabilized. Follow-up procedures in Section 7.3.1 must be followed.

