9.1 Sample Size

This is a single-arm trial to assess the effect of brexpiprazole on patient engagement in MDD patients through the following co-primary endpoints: 1) change from baseline to

Week 8 in IDS-SR-10-engagement; 2) change from baseline to Week 8 in IDS-SR Total score.

Based on the results of the appropriate brexpiprazole-plus-ADT arms from four previous Phase 2/3 brexpiprazole MDD trials, it is reasonable to expect a mean change of -2.5 (standard deviation = 6.5) in IDS-SR-10-engagement and a mean change of -5 (standard deviation = 13.5) in IDS-SR Total score from baseline to Week 8. A sample size of 100 completers (ie, patients who have an evaluation on IDS-SR Total score and IDS-SR-10-engagement at Week 8) will yield 95% power to show a difference from baseline in IDS-SR Total score and at least 95% power to show a difference from baseline in IDS-SR-10-engagement at a two-sided significance level of 0.05, respectively. It will ensure the overall power is at least 90%. After considering an ET rate of 25%, a total of 134 patients need to be enrolled in this trial.

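### The two-weekly mean daily dose in SAP 9.1 counts days after a patient's last dose as 0 mg, which lowers the reported mean and the low end of the range

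*SAP*

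**What the plan says.** SAP 9.1 sets fixed calendar blocks, illustrated as "study: ie, Day 1-14 in Week 1-2, Day 15-28 in Week 3-4, etc". For each patient and block it defines the mean daily dose this way: "This will be calculated by dividing the sum of individual total doses by the number of days in the biweekly interval". The table then gives the number of patients receiving drug and "the mean and range of the mean daily dose for every two weeks".

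The same section ends duration of exposure at the last day of drug, but the mean-daily-dose rule does not use that date. SAP 9 places all safety analyses on the Safety Sample, so early stoppers are included. Protocol 7.3.1 ends trial participation when treatment is discontinued.

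Early stopping is expected. Protocol 9.1 states: "After considering an ET rate of 25%, a total of 134 patients need to be enrolled in this trial". Protocol Table 1.3-1 allows visits to move by 5 days either way, and its footnote j says drug is not prescribed at the Week 8 visit.

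**The concern.** The interval in the rule is the 14-day block, so the divisor is 14 for everyone with at least one dose in it. Days after the last dose lie outside the patient's participation, yet they enter the average as zero-dose days. This affects every early terminator except those whose last dose falls on Day 14, 28 or 42. It also affects any completer whose last dose comes before Day 56.

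The resulting figure mixes two things: the dose the patient took and how long the patient stayed on drug. Duration of exposure already measures the second. The minimum suffers most, because one patient who stops early in a block can set it at a value that nobody was prescribed. A drop in the last block could also be misread as late down-titration.

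**Working it through.** **Figure stated in the plan.** SAP 9.1 gives no numerical result to reproduce. The related planning figure does reproduce: 100 / (1 − 0.25) = 133.3, rounded up to 134, so 134 − 100 = 34 early terminations are expected.

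**Inputs from the documents.** 14-day blocks and a divisor of 14 (SAP 9.1); 25% early termination (Protocol 9.1, SAP 4); doses of 0.5 to 2 mg after Week 2 and tablet strengths from 0.25 mg (SAP 3.2); ±5-day visit window (Protocol Table 1.3-1).

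**Assumptions, because the documents do not give them.** Constant dose; early terminators' last doses spread evenly over Days 1-50; several patterns for completers' last dose; 10% early termination as an alternative.

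**Single patient.** With constant dose d and k dosing days in the block, the SAP value is d × k/14. The value per day up to the last dose is d. At d = 2 mg:

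- Last dose Day 51, Days 43-56: k = 9, 18/14 = 1.29 mg.
- Last dose Day 17, Days 15-28: k = 3, 6/14 = 0.43 mg.
- Last dose Day 15, Days 15-28: k = 1, 2/14 = 0.14 mg, below the smallest tablet strength.

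**Cohort mean.** Among patients with at least one dose in the block, the ratio of reported to actual mean is

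(share stopping in block × their mean k/14 + share dosed past the block) / (sum of the two shares).

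For early terminators stopping on any of a block's 14 days with equal chance, mean k/14 = 7.5/14 = 0.536. At 25% early termination:

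- Days 15-28: stopping 0.25 × 14/50 = 0.07; continuing 0.75 + 0.25 × 22/50 = 0.86. Ratio (0.07 × 0.536 + 0.86)/0.93 = 0.965.
- Days 29-42: stopping 0.07; continuing 0.75 + 0.25 × 8/50 = 0.79. Ratio (0.07 × 0.536 + 0.79)/0.86 = 0.962.
- Days 43-56: early stoppers over Days 43-50 are 0.25 × 8/50 = 0.04, with mean k/14 = 4.5/14 = 0.321. Completers are 0.75, with mean k/14 = c. Ratio (0.04 × 0.321 + 0.75c)/0.79.

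The value of c depends on when completers take their last dose. It is 1 if all end on Day 56, 67/70 = 0.957 for Days 54-58, 92/98 = 0.939 for Days 53-59, and 139/154 = 0.903 for Days 51-61.

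| Block, true dose 2.000 mg, 25% early termination | Reported mean (mg) | Understated by |
|---|---|---|
| Days 15-28 | 1.930 | 3.5% |
| Days 29-42 | 1.924 | 3.8% |
| Days 43-56, completers end Day 56 | 1.931 | 3.4% |
| Days 43-56, completers end Days 54-58 | 1.850 | 7.5% |
| Days 43-56, completers end Days 53-59 | 1.815 | 9.2% |
| Days 43-56, completers end Days 51-61 | 1.746 | 12.7% |

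At 10% early termination the values are 1.973 (1.3% low), 1.972 (1.4% low) and, for the last block, 1.976 to 1.785 (1.2% to 10.8% low). The percentages hold for any constant dose. Dividing by days up to the last dose returns 2.000 in every case.

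**Share of early terminators affected.** Under the even spread, 3 of the 50 possible days (14, 28, 42) end a block, so 47/50 = 94% are affected.

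**The case against.** Several points can fairly be made for leaving the rule alone.

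- Dose per calendar day is a coherent quantity, openly defined, and could simply be labelled as such. That is true, but the table is confined to patients receiving drug in the block, and days after the last dose are not trial days for someone who has left. A label would disclose the mixture without separating it.
- The mean shifts little: about 3-4% with even stops and completers ending on Day 56, or roughly 0.07 mg on 2 mg. This stands. The maximum is also unchanged if any patient takes the top dose for a full block.
- The larger last-block figures rest on assumed last-dose days. This stands too. The ±5 days is a visit window, not a dosing rule, and the dosing table runs Week 8 as Days 50-56. If completers all end on Day 56 there is no late fall.
- Missed doses before the last dose would still count as zero, and Protocol 7.3.2 says "Brief treatment interruptions/periods of non-adherence will be allowed". At 2 mg, a patient dosed only on Days 15 and 28 would show 4/14 = 0.29 mg under either rule. That is deliberate: missed doses while on treatment are part of the dose received, and days after stopping are not.
- The block counts, overall duration and the compliance listing show attrition alongside. They do not correct the per-patient means.

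A programmer might read the rule as the patient's own days in the block, but the text does not say so.

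**Conclusion.** The concern holds on the plain wording of SAP 9.1. Followed as written, the rule understates the dose of any patient whose last dose falls inside a block, by a factor of k/14. The clearest damage is to the minimum, which can fall to 0.14 mg for a patient taking 2 mg. Under even stopping at 25% early termination the mean is 3.5% and 3.8% low in the second and third blocks, and 3.4% to 12.7% low in the last. The upper part of that last range depends entirely on the assumed timing of completers' last doses. The effect is confined to a descriptive exposure table: no test, alpha, power or safety criterion uses it. It should be corrected because it is the SAP's only by-period dose summary in a flexible-dose trial and the correction is nearly free.

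**What to change.** In SAP 9.1, replace the divisor with each patient's own days in the block. Count from the later of block start and first dose to the earlier of block end and last dose, among patients with at least one dose in the block. State that interruptions between first and last dose still count as zero-dose days. Keep duration of exposure as the separate measure of time on drug.

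The cost is one sentence in the SAP and one line of programming. No new data are needed, since Protocol 6.4 says: "The actual start and finish dates for each dose strength of trial drug administered will be recorded on the CRF".
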